**Part 1: General questions about yourself and your attitudes**

1. Are you

Female  
 Male

2. How old are you? \_\_\_\_\_ years

3. What is your highest level of education? (select only one option)

Primary school  
 Year 10 of secondary school (O-levels)  
 Completed secondary schools (Year 12, A-levels)  
 University/college degree  
 A different qualification \_\_\_\_\_

4. What is/was your occupation? (select only one option)

Farmer/agriculturalist  
 Independent professional (e.g., doctor, lawyer)  
 Self-employed  
 Civil servant/public official  
 Employee  
 Manual worker  
 Different occupation, namely \_\_\_\_\_

**ACCEPTANCE OF HEALTH CARE SECTOR APPLICATION  
(MY-AHA) FOR SMARTPHONES/TABLETS QUESTIONNAIRE (DART)**

**Part II: Questions regarding your use of My-AHA during the last few months**

	Non-existent / very poor	Very Good
1. How do you rate your skill with smartphones/tablets		
2. How do you rate your knowledge of smartphone applications from the health care sector? (e.g., nutrition assistant, movement assistant etc? )	     	
3. How often did you use the My-AHA application in the last few months?	 Not at all  Once a week  More than once a week  Daily	

**ACCEPTANCE OF HEALTH CARE SECTOR APPLICATION  
(MY-AHA) FOR SMARTPHONES/TABLETS QUESTIONNAIRE (DART)**

5. Would you be prepared to pay a **monthly** fee for using the My-AHA application?  
If so, how much would you be prepared to pay? *(select one option only)*

Less than \$5  
 Less than \$10  
 More than \$10  
 I would not be prepared to pay a monthly fee to use the application

6. Would you be prepared to pay a **one-off** fee for using the My-AHA application?  
If so, how much would you be prepared to pay? *(select one option only)*

Less than \$5  
 Less than \$10  
 More than \$10  
 I would not be prepared to pay a one-off fee to use the application

7. Would you buy the My-AHA application if it were partially financed by your health insurance fund?

Yes  
 No

**ACCEPTANCE OF HEALTH CARE SECTOR APPLICATION  
(MY-AHA) FOR SMARTPHONES/TABLETS QUESTIONNAIRE (DART)**

**Now please rate the importance of the following statements regarding smartphone/tablet applications in the health care sector**

The application should ....	Totally unimportant						Very important
help me improve my own personal fitness levels							
allow me an adequate level of self-control							
give me advance warning of health risks, thus improving my safety							
reward me appropriately for healthy behavior							
help me expand my knowledge of health issues							
enable me to talk about health-related topics with my family and friends							
enable my family and friends to support me with health issues							
enable the creation of groups of people with similar, health-related interests							
support me in making new contacts and getting to know them							
be modern, and designed according to the current state of the art							

**ACCEPTANCE OF HEALTH CARE SECTOR APPLICATION  
(MY-AHA) FOR SMARTPHONES/TABLETS QUESTIONNAIRE (DART)**

**Please rate the extent to which the My-AHA application that you have been using over the past few months corresponds to the statements below**

The application ....	Not at all					Fully
helps me to improve my personal fitness level						
allows me an adequate level of self-control						
improves my safety by warning me at an early stage of health risks						
rewards me appropriately for healthy behavior						
helps me expand my knowledge of health issues						
enables me to talk about health-related topics with my family and friends						
enables my family and friends to support me with health issues						
enables the creation of groups of people with similar, health-related interests						
supports me in making new contacts and getting to know them						
is modern, and designed according to the current state of the art						

**ACCEPTANCE OF HEALTH CARE SECTOR APPLICATION  
(MY-AHA) FOR SMARTPHONES/TABLETS QUESTIONNAIRE (DART)**

**Once again, please rate the importance of the following statements regarding smartphone/tablet applications in the health care sector**

The application should ....	Totally unimportant					Very important
be adaptable and individually adjustable to my needs						
be easy to understand						
react quickly and have a short charging time						
be robust with no malfunctions / as few malfunctions as possible						
be displayed large enough on the screen so that I can see everything						
be inexpensive to buy						
be easy to learn to use, without a great deal of effort						
be easy to maintain, without a great deal of effort (e.g., updating the app to a newer version)						
treat my personal details confidentially						
not patronize me or restrict my autonomy in any way						

**ACCEPTANCE OF HEALTH CARE SECTOR APPLICATION  
(MY-AHA) FOR SMARTPHONES/TABLETS QUESTIONNAIRE (DART)**

**Once again, please rate the extent to which the MyAHA application you have been using during the last few months corresponds to the statements below**

The application ....	Totally unimportant					Very important
is adaptable and individually adjustable to my needs						
is easy to understand						
reacts quickly and has a short charging time						
is robust and never / hardly ever malfunctions						
is displayed on the screen large enough so that I can see everything						
is inexpensive to buy ( optional question )						
can be learned easily, without a great deal of effort						
can be maintained, without a great deal of effort (e.g., updating the app to a newer version)						
gives me the feeling that my personal details are treated confidentially						
does not patronize me or restrict my autonomy in any way						

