#### 4 Participant randomization

Participants will be randomized into 2 study arms, with 50% of participants allocated to each arm:

- Study Arm 1: Control group (n = 25)
- Study Arm 2: My-AHA intervention group (n = 25)

Randomization will occur at each study site independently.

Initial randomization of participants at each site will occur on a 1 (control) : 1 (intervention) ratio, with allocation of participants to each treatment arm being undertaken using an alternating allocation sequence based on order of entry into the study (i.e. participant 1 – study arm 1; participant 2 – study arm 2; participant 3 – study arm 1; participant 4 – study arm 2, and so on).

Once recruitment and allocation to study arms of 20 participants has occurred at each site. The study site PI will submit to the RCT Study Coordinator basic demographic information on the 20 participants recruited and allocated to study arms. The demographic information required for each of the 20 participants is:

- Gender
- Age
- Highest education level

The RCT study coordinator will review the balance of participants across study arms for these demographic variables within each study site and advise the Principal Investigator of any adjustment to the allocation procedures for remaining participant assignment to treatment arms to ensure equivalence of study arms within each site.

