### 6.11.3 DART Questionnaire

The DART questionnaire surveys the participant's responses to the use of application in the health care sector and their experiences in using the My-AHA application.

- The survey comprises 3 parts:
- Part 1 - collects basic demographic information and responses to the value of the My-AHA application
- Part 2 – comprises 19 items in which the participant rates the level of importance of different features of smartphone or tablet applications in the health care sectors
- Part 3 – comprised the same 19 items repeated, but the participant is asked to respond with reference specifically to the My-AHA application.

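### The single-choice payment options in DART questions 5 and 6 overlap below $5 and leave out exactly $10, so the split of answers below $10 and the placing of $10 answers are ambiguous

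*Protocol*

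**What the plan says.** Protocol section 6.11.3 describes the DART as a survey of participants' reactions to health-care applications and to My-AHA. It says that one part "collects basic demographic information and responses to the value of the My-AHA application". It gives no scoring rule for the payment items and names no willingness-to-pay endpoint.

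The form is in Appendix 26. In Part II, question 5 asks about a monthly fee and question 6 about a one-off fee. Each continues with "If so, how much would you be prepared to pay" and an instruction to select a single option. The three payment options are the same in both questions: *Less than $5*, *Less than $10* and *More than $10*. The fourth option is a refusal. In question 5 it reads "I would not be prepared to pay a monthly fee to use the application", and in question 6 "I would not be prepared to pay a one-off fee to use the application".

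Question 7, on part-financing by a health insurance fund, is a yes/no item, so questions 5 and 6 are the only DART items that attach a dollar amount to the application. Table 6 marks the DART at one assessment point only.

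**The concern.** A single-choice item works when every possible answer matches exactly one option. Here the first payment option lies wholly inside the second, and the round figure used as the upper boundary belongs to no option. Someone prepared to pay $3 can truthfully tick either of the first two lines. Someone prepared to pay $10 can truthfully tick none.

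What is at stake is the price breakdown among those willing to pay something. The fault arises when the answer is recorded, so an analysis plan written later cannot repair it: once the form is completed, nothing on it shows whether a tick at *Less than $10* meant $3 or $8, or where a $10 respondent went. With one administration there is no second answer to check against.

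**Working it through.** The plan states no figure for these items, so there is none to reproduce. The check is logical, followed by a simple bound.

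**Step 1: printed options as conditions on the amount x.** From Appendix 26, questions 5 and 6: x < 5; x < 10 (no lower limit printed); x > 10.

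**Step 2: number of payment options that are literally true for each amount.**

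| Amount x a person would pay | True options as printed | True options after the fix |
|---|---|---|
| 0 < x < 5 | 2 | 1 |
| 5 ≤ x < 10 | 1 | 1 |
| x = 10 | 0 | 1 |
| x > 10 | 1 | 1 |

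The options are mutually exclusive and exhaustive only if the count is 1 in every row. As printed, this fails in two rows, in both questions. The last column uses the conditions x < 5, 5 ≤ x < 10 and x ≥ 10.

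**Step 3: what can still be read.** Refusing versus paying some fee is clear. On the literal wording, a tick at *Less than $5* means under $5 and a tick at *More than $10* means over $10, except that a $10 respondent may have been pushed into a neighbouring line. The tick at *Less than $10* is the uncertain one: literally 0 < x < 10, probably meant as 5 ≤ x < 10.

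**Step 4: bound on the share below $5.** Let N be the number answering, a the ticks at *Less than $5* and b the ticks at *Less than $10*. Leaving aside misplaced answers at exactly $10,

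a/N ≤ share below $5 ≤ (a + b)/N.

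Section 4 plans 25 participants in the My-AHA arm; take these as the respondents, N = 25. The counts a = 5 and b = 8 are assumed for illustration and come from no document:

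- lower end: 5/25 = 20%
- upper end: (5 + 8)/25 = 13/25 = 52%

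The lower end applies if everyone who ticked *Less than $10* meant $5 or more. The upper end needs all 8 to have meant less than $5. Each such person moves the share by 1/25 = 4 percentage points. A different b changes the width of the interval, which is b/N (here 8/25 = 32 percentage points).

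**The case against.** The best counter-argument is that the ambiguity is mostly formal. The question is naturally taken as asking for a ceiling, the options are listed in ascending order and only one may be chosen. A person with a $3 ceiling who sees *Less than $5* directly above *Less than $10* will normally tick the first, which leaves the second to mean $5 to under $10. This is the likely reading, and it puts the truth nearer 20% than 52% in the illustration. It does not dispose of the point: the lower bound is not printed, each respondent has to infer it, and the inference does nothing for exactly $10.

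A second objection is weight. Section 6.11.3 speaks of value only in general terms, and its wording concerns Part 1 whereas the payment items stand in Part II of the form. No passage plans a median price or a demand figure, and section 7 identifies development of clinical frailty as the adverse endpoint. All of this stands, and it is why the point is minor.

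A reader might go further and infer that the payment results cannot be read at all, or that 20% to 52% is the expected uncertainty. The documents support neither. The pay/refuse split survives intact, two of the three payment options have a clear literal meaning, and the range is an extreme bound on invented counts.

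**Conclusion.** The defect is real and limited. In both questions the options overlap below $5 and omit exactly $10, so the split of answers below $10 is not reliably identified and $10 answers have no proper place. The finding rests only on the printed options and the single-choice instruction. Its numerical size depends on counts that are not known; the worked range is a worst case. The frailty outcome, the sample size and the comparison of the arms are unaffected. It is worth correcting because the correction is cheap and exact, and it ranks as an optional improvement.

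**What to change.** In Appendix 26, DART questions 5 and 6, print the payment options as *Less than $5*, *$5 to less than $10* and *$10 or more*, and keep each question's refusal line as it stands. Two option lines change in each question; participants answer the same number of items.

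There are three small costs:

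- The form is a protocol appendix, and section 11.1.2 requires modifications to go to the ethics committee for approval before use.
- Sections 10.1 and 10.2 provide for combining data across sites. Any other site whose DART data are pooled needs the same bands; whether other sites use the present wording is not shown.
- Forms already completed cannot be split reliably below $10, and their $10 answers cannot be recovered. They can be merged with the new forms on paying versus not paying.

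### The final DART block asks how well the app fits each statement but prints importance anchors, leaving 10 of the 20 app ratings ambiguous

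*Protocol*

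**What the plan says.** Protocol section 6.11.3 describes DART as a survey in three parts. Part 2 "comprises 19 items in which the participant rates the level of importance of different features of smartphone or tablet applications". Part 3 repeats those items, but "the participant is asked to respond with reference specifically to the My-AHA application".

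The form in Appendix 26 splits this material into four rating blocks that alternate between importance and the app. The block that first rates the app is headed: "Please rate the extent to which the My-AHA application that you have been using over the past few months corresponds to the statements below". Its anchors are *Not at all* and *Fully*. The third block returns to importance: "Once again, please rate the importance of the following statements regarding smartphone/tablet applications in the health care sector". Its anchors are "Totally unimportant" and "Very important".

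The fourth block goes back to the app: "please rate the extent to which the MyAHA application you have been using during the last few months corresponds to the statements below". Its anchors are again "Totally unimportant" and "Very important". Nothing in section 6.11.3 or Appendix 26 explains why the two app blocks use different scales.

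**The concern.** The question and the answer scale in the final block measure different things. The question is about how far the app fits a description, and the scale is about how much something matters. A respondent who has just rated the parallel features for importance, on exactly these anchors, may do so again. Another may follow the instruction and read the right-hand end as full agreement. Both leave the same mark on the page.

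What is at stake is the meaning of the app ratings for ten features: adaptability, ease of understanding, speed, malfunctions, screen size, price, ease of learning, maintenance, confidentiality and autonomy. If the two readings are mixed in unknown proportion, a high mean on one of these items may reflect a good app or only a valued feature.

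**Working it through.** The protocol gives no figure to reproduce here. The check sets the four blocks of Appendix 26 side by side and counts the items.

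| Block | Task in the instruction | Stem | Printed anchors | Items |
|---|---|---|---|---|
| 1 | importance | application should | Totally unimportant / Very important | 10 |
| 2 | fit of the app | application | Not at all / Fully | 10 |
| 3 | importance | application should | Totally unimportant / Very important | 10 |
| 4 | fit of the app | application | Totally unimportant / Very important | 10 |

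Blocks 1 to 3 each have anchors that suit their task. Block 4 has the task and stem of block 2 and the anchors of block 3. The instruction, stem, anchors and items of block 4 are all legible, so this is not a gap left by reading the PDF.

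**Share affected.** App-rating items: 10 + 10 = 20, of which 10 are in block 4, so 10/20 = 50%. One block 4 item, on price, is marked optional. Without it the count is (10 − 1)/(20 − 1) = 9/19 = 47%.

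**Importance/app pairs.** There are 20 pairs. The ten formed by blocks 1 and 2 are sound, and the ten formed by blocks 3 and 4 carry the ambiguity.

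**What the ambiguity does.** As an illustration, suppose a proportion p of respondents rate importance again in block 4 and the rest rate fit. Let I be the mean importance and C the mean fit of an item, and assume that both groups share these means. The expected block 4 mean is then (1 − p)C + pI. The difference between importance and app rating becomes I − [(1 − p)C + pI] = (1 − p)(I − C). It shrinks towards zero by an amount set by p, and the form provides nothing from which p could be estimated. Matching answers in blocks 3 and 4 would not identify the misreaders, because a good app with valued features gives the same pattern.

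**Part and item counts.** Section 6.11.3 says three parts and 19 items. The form announces two parts and prints 20 importance items and 20 app items. The optional price item could explain 19 on the app side. It does not explain 19 on the importance side, where the price item is not marked optional. None of this affects how a rating is read.

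**The case against.** A reader might infer that the block cannot be interpreted at all, that the comparison of wanted with delivered features is lost, and that no analysis could recover it. The documents do not support that much.

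- **Cues to the intended meaning.** The instruction asks about fit, the stem drops *should*, and the items are worded as descriptions of the app. The opening words of the instruction recall a task already done on the same form with suitable anchors. Both scales run from low to high in the same direction. Many respondents may answer as intended. This stands, and it makes the ratings ambiguous rather than meaningless.
- **No stated comparison.** Section 6.11.3 gives the paired structure but names no gap score, paired analysis or endpoint. Setting importance against delivery is a natural use of the form, not a stated purpose. This stands too, and the ten pairs from blocks 1 and 2 remain usable for it.
- **Overlap with other scales.** The SUS (Appendix 25) asks about ease of use, need for technical help, instability and learnability. The UEQ (Appendix 27) covers understandability, ease of learning, speed and security. This stands in part. Confidentiality is matched only loosely, screen size and autonomy are not matched, and neither scale provides DART's importance pairing.
- **Little depends on it.** DART plays no part in the pre-frailty criteria or in safety. Its app ratings apply to people who used the platform, chiefly the intervention arm of 25. This stands and sets the weight.

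None of these points removes the mismatch between question and scale. Nor do the documents show how it arose. It looks like a carry-over from the block before, but that is an inference.

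**Conclusion.** The point holds as an internal inconsistency on a participant-facing form. As printed, 10 of 20 app ratings (9 of 19 without the optional price item) allow two readings that the completed form cannot separate. They cannot be reliably pooled with the other app block or compared with their importance ratings.

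This rests on two assumptions: that the form is used as printed, and that staff do not correct the scale verbally, for which the protocol gives no instruction. How many respondents would misread the scale is unknown, so the size of any distortion cannot be stated.

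The weight is low: a form correction that leaves the trial's frailty outcome and its comparison of arms untouched. The mismatch in part and item counts is a clerical side point.

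**What to change.** On the final block of Appendix 26, replace the two printed anchors with *Not at all* and *Fully*, as on the form's other app-rating block, before the form is used. While the form is open, align the number of parts and items in section 6.11.3 with Appendix 26, and say whether the optional price item counts.

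If any forms have already been completed on the present scale, record which version each participant answered, keep those block 4 ratings separate, and report them with the ambiguity stated.

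The cost is two labels and a few words of description. No visit, procedure or sample size changes. Section 11.1.2 requires modified documents to go to the ethics committee before implementation, so the correction is best sent with the next submission that precedes use of the form.

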**Appendix 27. User Experience Questionnaire (UEQ)**

**USER EXPERIENCE QUESTIONNAIRE (UEQ)****PARTICIPANT CODE:** \_\_\_\_\_**STUDY SITE:** \_\_\_\_\_**TEST PHASE:** Baseline / 6 mo / 12 mo / 18 mo (circle one)

For the assessment of the My-AHA application, please complete the following questionnaire. The questionnaire consists a series of paired contrasting attributes that may apply to the My-AHA application. The circles between each paired attribute represent graduations between opposing attributes. You can express your agreement with the attributes by ticking the circle that most closely reflects your impression.

For example: attractive         unattractive

This response would mean that you rate the application as more attractive than unattractive.

Please decide spontaneously. Don't think too long about your decision to ensure that you convey your initial impression.

Sometimes you may not be completely certain about your agree with a particular attribute or you may find that the attribute does not apply completely to the My-AHA application. Nonetheless, please select a response for every statement.

It is your personal impressions that count, there are no right or wrong answers.

## USER EXPERIENCE QUESTIONNAIRE (UEQ)

Please assess the My-AHA application by ticking one circle in each line:

	1	2	3	4	5	6	7	
annoying		enjoyable						
not understandable		understandable						
creative		dull						
easy to learn		difficult to learn						
valuable		inferior						
boring		exciting						
not interesting		interesting						
unpredictable		predictable						
fast		slow						
inventive		conventional						
obstructive		supportive						
good		bad						
complicated		easy						
unlikable		pleasing						
usual		leading edge						
unpleasant		pleasant						
secure		not secure						
motivating		demotivating						
meets expectations		does not meet expectations						
inefficient		efficient						
clear		confusing						
impractical		practical						
organized		cluttered						
attractive		unattractive						
friendly		unfriendly						
conservative		innovative
